9.4.2 Methods of Analyses

9.4.2.1 General Considerations

Summary statistics will be computed by treatment group and visit. For continuous endpoints, the following descriptive statistics will be computed: number of observations, means, medians, standard deviations, standard errors, first and third quartiles, minimums and maximums, and 2-sided 95% CIs of the means (CIs will be provided for efficacy endpoints only). For categorical endpoints, the summaries will contain the number and percentage of subjects in each category.

The primary analysis method utilizing a repeated measures linear mixed effects model will include all observed data regardless of treatment adherence.

A sequential testing procedure will be used to maintain the family-wise type 1 error $\alpha = 0.05$ between the primary and secondary endpoints following the prespecified order below. An endpoint will only be tested for statistical significance if the endpoint tested in the previous step is statistically significant at 2-sided significance level of 0.05.

1. Primary endpoint: change from baseline in mean monthly hours of at least moderate headache pain intensity over months 1, 2, and 3

- 2. Secondary endpoints: change from baseline in mean monthly function domain score over months 1, 2, and 3, as measured by the MFIQ using the Hochberg procedure
 - Impact on physical functioning
 - Impact on usual activities
 - Impact on emotional functioning
 - Impact on social functioning
- Secondary endpoint: change from baseline in mean monthly average duration of at least moderate pain intensity in migraine attacks occuring over months 1, 2, and 3 (migraine attacks as defined in Section 11.1)
- 4. Secondary endpoint: change from baseline in mean monthly average peak migraine pain intensity over months 1, 2, and 3, as assessed by the 11-point NRS

Endpoint	Statistical Analysis Methods
Primary	The primary endpoint will be analyzed using a linear mixed effects model including treatment group, baseline value, scheduled visit, and the interaction of treatment group with scheduled visit, without any imputation for missing data.
Secondary	The secondary endpoints will be analyzed using a linear mixed effects model including treatment group, baseline value, scheduled visit, and the interaction of treatment group with scheduled visit, without any imputation for missing data.
Exploratory	Detailed primary analysis method for exploratory endpoints will be described in the SAP.

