3.2 Sample Size

A total sample size of 576 subjects (288 subjects per group including 10% dropouts) provides at least a 90% power for the primary efficacy hypothesis. The statistical power for secondary efficacy hypotheses ranges from 81% to > 99% (Table 3-1).

Table 3-1. Sample Size Assumptions and Statistical Powers for Primary and
Secondary Efficacy Endpoints for a Total Sample Size of 576 Subjects
Including a 10% Attrition Rate due to Dropout

Hypothesis	Assumed Treatment Effect	Power
------------	--------------------------------	-------

	(Common SD)	
Primary:	-16.7 (50)	96%
Change from baseline in mean monthly hours of at least moderate headache pain intensity over months 1, 2, and 3		
Secondary: Change from baseline in mean monthly		
MFIQ physical function domain score over months 1, 2, and 3	-9.2 (18.0)	> 99%
MFIQ usual activities domain score over months 1, 2, and 3	-7.5 (19)	> 99%
MFIQ emotional function domain score over months 1, 2, and 3	-11.5 (22)	> 99%
MFIQ social function domain score over months 1, 2, and 3	-6.9 (20)	97%
Average duration of at least moderate migraine pain intensity in migraine attacks occurring over months 1, 2, and 3 ^a	-2.0 (8)	81%
Average peak migraine pain intensity over months 1, 2, and 3	-0.11 (0.44)	81%

MFIQ = Migraine Functional Impact Questionnaire

Note: All power calculations are based on a 2-sided significance level of 0.05. The assumed treatment effects and common standard deviations are derived or chosen from a subset of placebo-treated and erenumab-140mg-treated subjects in erenumab Study 20120296 with high-frequency episodic migraine (ie, 7 to 14 monthly migraine days) and having at least 4 moderate-to-severe migraine attacks at baseline. ^a If a subject did not have any migraine attacks in a given month, the duration of at least moderate migraine pain intensity **was counted as 0**.

4. Covariates and Subgroups

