9.1 General Considerations

Summary statistics will be computed by treatment group and visit. For continuous endpoints, the following descriptive statistics will be computed: number of observations, means, medians, standard deviations, standard errors, first and third quartiles, minimums and maximums, and 2-sided 95% confidence intervals (CIs) of the means (CIs will be provided for efficacy endpoints only). For categorical endpoints, the summaries will contain the number and percentage of subjects in each category.

For the primary and secondary endpoints, the primary analysis method utilizing a repeated measures linear mixed effects model will include all observed data regardless of treatment adherence.

A sequential testing procedure will be used to maintain the family-wise type 1 error $\alpha = 0.05$ between the primary and secondary endpoints following the prespecified order below. An endpoint will only be tested for statistical significance if the endpoint tested in the previous step is statistically significant at 2-sided significance level of 0.05.

- 1. Primary endpoint: change from baseline in mean monthly hours of at least moderate headache pain intensity over months 1, 2, and 3
- Secondary endpoints: change from baseline in mean monthly function over months 1, 2, and 3, as measured by the MFIQ using the Hochberg procedure
 - Impact on physical functioning

- Impact on usual activities
- Impact on emotional functioning
- Impact on social functioning
- 3. Secondary endpoint: change from baseline in mean monthly average duration of at least moderate pain intensity **in** migraine attack**s** over months 1, 2, and 3
- 4. Secondary endpoint: change from baseline in mean monthly peak migraine pain intensity over months 1, 2, and 3, as assessed by the 11-point NRS

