9.5 Efficacy Analyses

The primary and secondary efficacy analyses will utilize the M-DBTP EAS and the exploratory efficacy analyses will utilize the E-DBTP EAS. Subjects will be analyzed according to their randomized treatment group regardless of the actual treatment received during the study.

Detailed efficacy analysis methods and covariates included in the models are summarized in the table below.

Endpoint	Primary Summary and Analysis Method
Change from baseline in mean monthly hours of at least moderate headache pain intensity over months 1, 2, and 3	 Summary statistics by visit using observed data at each visit and the calculated mean monthly hours of headache pain over months 1, 2, and 3
	2. Least squares means from a linear mixed effect model including treatment group, scheduled visit, interaction of treatment and scheduled visit and baseline value using observed data
	 Estimate treatment difference (AMG 334 – Placebo) from the model in #2.

Table 9-1. Primary Efficacy Endpoint Summary Table

Table 9-2. Secondary Efficacy Endpoint Summary Table

Т

Endpoint	Primary Summary and Analysis Method
Change from baseline in mean monthly function as measured by the Migraine Functional Impact Questionnaire (MFIQ) over months	 Summary statistics by visit using observed data at each visit, and the calculated mean monthly values over months 1, 2 and 3
1, 2, and 3; Change from baseline in mean	 Least squares means from a linear mixed effect model including treatment group, scheduled visit, interaction of treatment and scheduled visit and baseline value using observed data
monthly average duration of at least moderate pain intensity in migraine attack s over months 1, 2, and 3;	 Estimate treatment difference (AMG 334 – Placebo) from the model in #2
Change from baseline in mean monthly peak migraine pain intensity as assessed by the 11-point Numeric Rating Scale (NRS) over months 1, 2, and 3	

Endpoint	Primary Summary and Analysis Method
Change from baseline in mean MMD over months 1, 2, and 3 ^a	 Summary statistics by visit using observed data at each visit and the calculated mean monthly migraine day over months 1, 2, and 3 Least squares means from a linear mixed effect model including treatment group, scheduled visit, interaction of treatment and scheduled visit and baseline value using observed data Estimate treatment difference (AMG 334 – Placebo) from the model in #2.

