9.5.1 Analyses of Primary and Secondary Efficacy Endpoints

For the primary and secondary endpoints will be tested using a linear mixed model based on observed monthly data with appropriate contrasts for pairwise treatment comparisons.

The model will include treatment, scheduled visit, treatment by visit interaction, and baseline value as covariates. If applicable, the first-order autoregressive covariance structure is assumed. Least squares means (LSMs) for each treatment group, standard errors, associated 95% CIs, difference of LSMs compared to placebo group, associated 95% CIs and nominal two-sided p-values will be tabulated by visit and treatment, as well as for the mean monthly values over months 1, 2, and 3 of the DBTP. No sensitivity analyses will be performed for the primary and secondary endpoints.

Subgroup analysis described below will be performed for the primary and secondary endpoints:

- 1. Treatment failure of prior migraine prophylactic medications (1, 2, and 3 or more treatment failures)
- 2. Medication overuse at baseline (yes vs. no)

The purpose of the subgroup analyses is to explore if the treatment effect varies across subgroups of interest. Subgroup analyses are performed for primary and secondary efficacy endpoints using the same method as primary analysis method but performed within each interested subgroup.

The heterogeneity of the treatment effect across the subgroups will be evaluated by examining the treatment-by-subgroup interaction at primary time point and an interaction p-value will be presented. The primary analysis model with the addition of treatment-by-subgroup interaction will be used.

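### SAP 9.5.1 names only AR(1), under an undefined condition, for the three-visit primary and secondary models; if its constraints fail, the standard error is typically 1–5% off, in a direction the documents cannot settle

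*SAP*

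**What the plan says.** SAP 9.5.1 makes the only covariance statement for the primary and secondary models in either document: "If applicable, the first-order autoregressive covariance structure is assumed". The same section adds "No sensitivity analyses will be performed for the primary and secondary endpoints". It tabulates LS means, standard errors, confidence intervals and nominal p-values by visit and for the mean over months 1 to 3.

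The model is described elsewhere by its fixed effects alone. SAP Tables 9-1 and 9-2 give a "linear mixed effect model including treatment group, scheduled visit, interaction of treatment and scheduled visit and baseline value using observed data", protocol 9.4.2 has the same terms ("using a linear mixed effects model including treatment group, baseline value, scheduled visit, and the interaction of treatment group with scheduled visit"), and SAP 9.1 refers to "utilizing a repeated measures linear mixed effects model". No random effect, alternative structure, convergence fallback, sandwich variance or degrees-of-freedom method is named.

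Two nearby SAP provisions deal with other problems: 8.5 (ad hoc analyses for extreme values) and 8.6 (transformation or a rank method for non-normality).

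**The concern.** Used alone, AR(1) imposes two constraints on three visits: equal variance in months 1, 2 and 3, and a month 1–month 3 correlation equal to the square of the adjacent-month correlation. If either fails, the model-based standard error, interval and p-value of the 3-month mean are off. With complete data the point estimate is essentially unaffected, so precision is what is at stake.

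The undefined condition adds a second problem. Two statisticians following this text could fit AR(1), AR(1) with a random intercept, or something else, and report different p-values. Nothing in the text fixes that choice before unblinding. The primary p-value opens the testing sequence in SAP 9.1, and every secondary endpoint uses the same model.

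**Working it through.** **Inputs from the documents.** "A total sample size of 576 subjects (288 subjects per group including 10% dropouts" (SAP 3.2), so 288 × 0.9 ≈ 259 evaluable per arm, 518 in all. "All power calculations are based on a 2-sided significance level of 0.05". Primary effect −16.7 hours, SD 50. Attack duration −2.0, SD 8. Peak pain −0.11, SD 0.44.

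**Inputs assumed.** Between-month correlations and relative monthly SDs (residual, after baseline adjustment), because the documents give none.

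**The plan's own figures first.**
- Primary: SE = 50 × √(2/259) = 4.39. z = 16.7/4.39 = 3.80. Power = Φ(3.80 − 1.96) = 96.7% (plan: 96%).
- Duration: 2.0/(8 × √(2/259)) = 2.845. Φ(2.845 − 1.96) = 81.2% (plan: 81%). Peak pain gives the same, since 0.11/0.44 = 2.0/8. This matches "The statistical power for secondary efficacy hypotheses ranges from 81% to > 99".

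These are two-sample calculations that do not use the covariance structure, so the sample size is not in question.

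**Method.** For an assumed true 3×3 covariance, find the AR(1) variance and correlation that the Gaussian likelihood converges to. Then take k = (AR(1) model-based SE)/(true SE) for the 3-month mean. The true type I error of a nominal 5% test is 2 × [1 − Φ(1.96k)]. Data are complete and there is no random effect.

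**Equal variances.** The fitted correlation is the adjacent-month correlation r. With month 1–month 3 correlation s, k² = (3 + 4r + 2r²)/(3 + 4r + 2s).
- Flat 0.4: k² = 4.92/5.40, k = 0.954, type I error 6.1%.
- Flat 0.8: k² = 7.48/7.80, k = 0.979, type I error 5.5%.
- r = 0.6, s = 0.25: k² = 6.12/5.90, k = 1.018, type I error 4.6%.

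**Unequal variances (AR(1) fitted numerically).**

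| True correlation | Monthly SDs | Type I error |
|---|---|---|
| AR(1), 0.4–0.8 | 1.3, 1, 1 | 4.2–4.6% (k 1.020–1.036) |
| Flat 0.4 | 1.3, 1, 1 | 5.7% (k 0.971) |
| AR(1), 0.4–0.8 | 1, 0.9, 0.8 | 4.9–5.0% |
| Flat, 0.4–0.8 | 1, 0.9, 0.8 | 5.4–6.1% |
| Flat 0.8 | 1, 1.3, 1 | 7.2% |

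The last row in full: the fit is variance 1.128 and correlation 0.738. The model-based sum is 1.128 × (3 + 4 × 0.738 + 2 × 0.738²) = 7.94. The true sum is 3.69 + 2 × (1.04 + 1.04 + 0.80) = 9.45. So k = √(7.94/9.45) = 0.917.

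**By visit.** AR(1) pools one variance. With SDs 1, 0.9, 0.8 it is about (1 + 0.81 + 0.64)/3 = 0.817, an SD of 0.904. The month 1 SE is then 0.904/1, about 10% too small, and the month 3 SE is 0.904/0.8 = 1.13, about 13% too large, even where the 3-month mean is barely affected.

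**Consequence for results.** Hold the true SE at its planned value and let the reported SE be k times that.
- Primary: the reported SE is 4.39 × 0.954 = 4.19 for flat 0.4, and 4.39 × 1.036 = 4.55 at k = 1.036. The 95% half-width is 8.2 or 8.9 against a correct 8.6.
- An 81%-power secondary: the chance of nominal significance is Φ(2.845 − 1.96k), which is 83.5% at k = 0.954, 79.2% at k = 1.036 and 85.3% at k = 0.917.

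**Simulation** with the baseline covariate in the model (20,000 trials, 259 per arm; Monte Carlo SE about 0.16 points): flat 0.4 gave 6.2% with AR(1) and 5.0% unstructured. With AR(1) true at 0.6 the figures were 5.1% and 5.2%.

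**The case against.** AR(1) is a legitimate prespecification for visits about four weeks apart, and every misfit above is assumed. That stands. A reader might infer that AR(1) is the wrong structure here or that the primary test is anti-conservative. The documents support neither, because they contain nothing on monthly variances or correlations and the error can go either way.

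The consequence is small. The primary conclusion barely moves at the planned effect. The two 81%-power endpoints are steps 3 and 4, reached only after the primary and the MFIQ step. The by-visit p-values are nominal and outside the sequence. This stands too, and it sets the weight of the point.

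The 7% case needs month 2 alone to have 69% more variance (1.3² = 1.69) on top of flat correlation. The documents give no reason to expect that, so it shows only that the milder figures are not limits.

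The word *mixed* may imply a subject random intercept. None is stated. One would bring the flat case back to 5.0%, but with AR(1) correlation and SDs 1.3, 1, 1 the type I error would stay at 4.2–4.6%, and with lag correlations 0.6 and 0.25 at 4.6%. The gap remains on either reading.

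**Conclusion.** The point holds as a cheap improvement. The undefined condition is a real gap in the text. The numerical consequence is conditional: if equal variances or geometric decay fail, the SE of the 3-month mean is typically 1–5% off, with the sign unknown. This rests on assumed covariances, complete data and AR(1) without a random effect. In the flat-correlation case, 10% dropout at random leaves the type I error at 5.5–6.1%.

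A reader might also infer that a steady trend in monthly SDs is harmless. That is so only when the correlation itself is AR(1).

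**What to change.** In SAP 9.5.1, delete *If applicable* and replace the sentence with:

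*An unstructured within-subject covariance matrix (3 visits), with no subject random effect and Kenward-Roger degrees of freedom, will be used; if it does not converge, heterogeneous Toeplitz with sandwich standard errors will be used.*

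This takes one sentence and a line of code, and should be settled before unblinding. It uses six covariance parameters instead of two, with about 518 evaluable subjects. Intervals become slightly wider where AR(1) would have understated the SE (2–5% for flat 0.4–0.8, from 1/0.979 and 1/0.954), about 2% narrower under the faster decay, and unchanged on average if AR(1) is true. In a subgroup of 26 per arm, the unstructured model kept type I error at 5.1–5.2%.

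Non-convergence with three visits is unlikely. If the fallback is used, the sandwich variance corrects the standard error only. It does not remove any effect of a wrong working covariance on the estimate when data are incomplete.

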9.5.2 M-DBTP Analyses of Exploratory Efficacy Endpoints

For exploratory efficacy endpoints during the M-DBTP, summary statistics and primary analysis method will be conduct in the same way as that for the primary and secondary endpoints.

The continuous exploratory efficacy endpoints at each assessment time point or over months 1, 2, and 3 of the 3-month M-DBTP will be analyzed using the

linear mixed effects model that includes treatment group, baseline values, scheduled visit, and the interaction of treatment and scheduled visit without any imputation for missing data.

The efficacy endpoints for PCS total score and PGI-S score will be analyzed using analysis of covariance model including treatment and baseline value as covariates. The efficacy endpoints for **MTS** (achievement of "Very Much Improved" or "Much Improved") and the MIBS (achievement of no or mild interictal burden) will be analyzed using logistic regression model with missing data imputed using NRI **up to End of Study Date**. No sensitivity analyses will be performed for the exploratory endpoints.

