9.3.4 Handling of Missing and Incomplete Data

Subjects may miss specific data points for a variety of reasons. In general, data could be missing due to a subject's early withdrawal from the study, a missed visit, or inability to evaluate an endpoint at a time point. For this study, efficacy endpoints will be collected via eDiary and subjects could miss entering several days of data in each monthly interval. The general procedures outlined below describe how missing data will be handled.

For the endpoints derived from daily diary during month 1 to 3, if at least 14 days of eDiary are collected in the monthly interval, then the monthly frequency measurements (eg, migraine days, headache days) will be prorated based on the number of days with available information.

Missing items in each clinical outcome assessment questionnaire will be handled based on the scoring algorithm for each assessment.

Missing data after above methods will either be handled by the linear mixed effects model under missing-at-random assumption or imputed as non-responders for binary endpoint.

Missing data in safety data will not be imputed.

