5.2 Study Dates

Informed Consent Date

The date on which subject signs the informed consent form.

Date of Ready for Daily Diary Entry in Baseline

The date on which an eDiary device is ready for daily diary entry after completion of run-in period.

Randomization Date

Randomization Date is defined as the date subject was allocated to a treatment group.

Enrollment Date

Enrollment Date is defined as the randomization date.

First IP Dose Date

First IP Dose Date is the date on which a subject is administered the first dose of IP following randomization as recorded on the IP Administration eCRF. The first IP dose may be the same day or after the randomization date.

Last IP Dose Date

Last IP Dose Date is the date on which a subject is administered the last dose of IP as recorded on the IP Administration eCRF.

End of Study (EOS) Date

End of study (EOS) date is defined as the last date on which the subject participates in the study as recorded on the End of Study eCRF.

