5.5 Subject Disposition

Randomized

Individuals are considered randomized if they have been assigned a randomization number. Randomized individuals are referred to as "subjects".

Exposed to Investigational Product

Subjects are defined as exposed if they receive at least one dose of investigational product.

Completing Investigational Product

Subjects are defined as completing investigational product if the primary reason for ending IP on End of IP eCRF is "Completed".

Completing Study

Subjects are defined as completing study if they complete the entire 16 weeks of study evaluation. It will be derived from the End of Study eCRF with "Completed" as the primary reason for ending study.

On Study

Subjects are defined as on study for specific study week if their end of study date is on or after the first day of the analysis window.

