Change from baseline in pain catastrophizing as measured by the Pain Catastrophizing Scale (PCS) at month 3 ^b	 Summary statistics using observed data at week 12 Analysis of covariance (ANCOVA) model including treatment group and baseline value using observed data Estimate treatment difference (AMG 334 – Placebo) using the model in #2.
Achievement of no or mild interictal burden as measured by the MIBS-4 at assessment time points ^c	 Summary statistics using observed data at the specific month Logistic regression model including treatment group and baseline value will be used after subjects with missing outcome data are imputed as non-responders (NRI)

Table 9-3. Exploratory Efficacy Endpoint Summary Table

Endpoint	Primary Summary and Analysis Method	
Achievement of pain freedom at 2 hours post-triptan dose for the first attack at month 4 ^d	Summary sta assessment f	itistics using observed data at the time points
	group will be	ession model including treatment used after subjects with missing ment are imputed as non-responders
Use of migraine rescue medication within 24 hours post-triptan dose for the first attack at month 4	Summary sta assessment	atistics using observed data at the time points
		ression model including treatment observed data
^a The same analyses methods will be applie	the endpoints:	

The same analyses methods will be applied to the endpoints:

Change from baseline in mean monthly hours of at least moderate pain intensity for qualifying oral triptan-treated migraine attacks over months 1, 2, and 3

Change from baseline in mean average duration of at least moderate pain intensity for qualifying oral triptan-treated migraine attacks occurring over months 1, 2, and 3

Change from baseline in Migraine Symptom Severity Score (MSSS) total score at assessment time points Change from baseline in mean monthly total migraine freedom days over months 1, 2, and 3

Change from baseline in Migraine Interictal Burden Scale (MIBS-4) total score at assessment time points (the model will include data at month 1-4)

Change from baseline in headache impact scores as measured by the Headache Impact Test (HIT-6) total score at assessment time points

Change from baseline in physical function domain score as measured by MFIQ at assessment time points Change from baseline in usual activities domain score as measured by MFIQ at assessment time points

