9.7 Other Analyses

Not Applicable.

10. Changes From Protocol-specified Analyses

There are one deviation from protocol:

• The efficacy analysis set mentioned in protocol was changed to M-DBTP efficacy analysis set and E-DBTP efficacy analysis set to meet the target population of primary, secondary and exploratory endpoints.

11. Literature Citations / References

Quade, D. (1966), Rank analysis of covariance, University of North Carolina, Institute of Statistics Mimeo Series. No. 483

12. Data Not Covered by This Plan

There are no plans to specifically analyze or summarize the following data points.

13. Appendices

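### SAP 9.5.2 stops non-responder imputation at each subject's End of Study date, so subjects who leave before a visit window drop out of the MTS and MIBS-4 responder analyses, in conflict with SAP Table 9-3 and Protocol 9.3.4.

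*SAP*

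**What the plan says.** SAP 9.5.2 analyses the MTS and MIBS-4 responder endpoints by logistic regression, with missing data set to non-response (NRI) "up to End of Study Date". SAP 9.5.3 repeats the limit for the dichotomous month-4 endpoints.

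The SAP treats this date as a property of the subject. Section 5.2 says that it "is defined as the last date on which the subject participates in the study". Section 5.5 counts a subject as on study for a given week "if their end of study date is on or after the first day of the analysis window".

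Two other places give the rule without a limit:
- Protocol 9.3.4 lists the sources of missing data as "early withdrawal from the study, a missed visit, or inability to evaluate an endpoint" at a time point. What remains missing is handled by the mixed model "or imputed as non-responders for binary endpoint".
- SAP Table 9-3, in the MIBS-4 row, fits the logistic model after "subjects with missing outcome data are imputed as non-responders (NRI"). Footnote c applies the same method to MTS.

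SAP Section 10 states "There are one deviation from protocol" and names only the change of efficacy analysis sets.

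**The concern.** NRI exists mainly for subjects who leave and cannot be assessed. If it ends on the day a subject leaves, later visits have neither an observed nor an imputed outcome, and the logistic regression omits the subject. For those visits the response rate is calculated among subjects still on study, although Table 9-3 describes a rate among all subjects with missing outcomes counted as failures.

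A programmer cannot follow both 9.5.2 and Table 9-3. If the choice is made after unblinding, it is made with the results in view. SAP 9.5.2 also rules out sensitivity analyses for the exploratory endpoints, so no other planned output would show how much the rule matters.

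**Working it through.** **1. Which visits are lost.** Inputs: visit windows from SAP Tables 5-3 and 5-5 (week 4, days 16 to 43; week 8, days 44 to 71; week 12, days 72 to 99), the on-study rule in SAP 5.5, and Protocol 8.1.5. Protocol 8.1.5 places the end-of-study visit 4 weeks after the last dose for subjects who discontinue the study, with the week 12 assessments done at an early termination visit. If that visit is kept:

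| Last dose | End-of-study visit, about | On study for week 8? | On study for week 12? |
|---|---|---|---|
| Day 1 | day 1 + 28 = day 29 | no | no |
| Week 4 (day 29) | day 29 + 28 = day 57 | yes | no |
| Week 8 (day 57) | day 57 + 28 = day 85 | yes | yes |

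The week 12 loss therefore concerns subjects whose End of Study date is before day 72. Those who withdraw consent or are lost at once can have an earlier date than the table shows. MTS is the more exposed endpoint because it has only the week 12 window: an MTS answer given at a termination visit on day 57 maps to no analysis visit, whereas a MIBS-4 answer that day maps to week 8.

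**2. How many subjects.** Inputs: 288 per arm and 10% dropout (SAP 3.2). The plan gives no figure for the responder endpoints, but its power table confirms how it applies the dropout.
- Evaluable per arm: 288 × 0.90 = 259.2, or about 259.
- Primary endpoint: Φ(16.7 / (50 × √(2/259)) − 1.96) = Φ(3.80 − 1.96) = 96.7%, against 96% stated.
- Average attack duration: Φ(2.0 / (8 × √(2/259)) − 1.96) = Φ(2.845 − 1.96) = 81.2%, against 81% stated. With 288 per arm it would be 85.1%, so the table does rest on 259.

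The upper bound is then 288 − 259 = 29 per arm, or about 58 of 576, if dropout is equal. The true number is smaller, because 10% covers the whole study and not only departures before day 72.

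**3. What it does to the estimate.** Let p be the response rate among assessed subjects and d the share whose End of Study date precedes the window. The limited rule reports p on N(1 − d) subjects. Full NRI reports p(1 − d) on N. The ratio of the two arms' rates under full NRI is (p₁/p₂) × (1 − d₁)/(1 − d₂), so the limited rule is more favourable to the arm with the larger d. The response rates and arm splits below are assumptions.

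| p, erenumab / placebo | d, erenumab / placebo | Limited rule, odds ratio | Full NRI, rates | Full NRI, odds ratio |
|---|---|---|---|---|
| 50% / 35% | 10% / 10% | 1.86 | 45.0% / 31.5% | 1.78 |
| 50% / 35% | 5% / 15% | 1.86 | 47.5% / 29.75% | 2.14 |
| 50% / 35% | 15% / 5% | 1.86 | 42.5% / 33.25% | 1.48 |
| 40% / 40% | 5% / 15% | 1.00 | 38.0% / 34.0% | 1.19 |
| 40% / 40% | 15% / 5% | 1.00 | 34.0% / 38.0% | 0.84 |

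First row worked: (0.50/0.50)/(0.35/0.65) = 1.86, and (0.45/0.55)/(0.315/0.685) = 1.78.

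**The case against.** The best defence is that Protocol 9.4.2.1 leaves the detailed methods for exploratory endpoints to the SAP, and Protocol 9.3.4 calls its rules general procedures. On that view a limit in the SAP is a permitted refinement. This stands in part: the gap in Section 10 is then a matter of documentation. It does not explain why the SAP's own Table 9-3 gives a different rule.

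A second defence reads End of Study as the study-level date in Protocol 4.4.1 (last subject, last visit), which would make the phrase harmless. SAP 5.2 defines it per subject and SAP 5.5 uses it that way, so this reading fails.

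The limits on size also stand. The endpoints are exploratory and outside the testing sequence. Visits before departure still count. At equal dropout the odds ratio moves only from 1.86 to 1.78 under the assumed rates; larger shifts need unequal dropout, on which the documents say nothing.

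A reader might go further in four ways that the documents do not support:
- *That the phrase turns the month-4 endpoints into completer rates.* SAP 6.3 already restricts that set to subjects who received the week 12 dose, and SAP 2.1 defines the acute-response endpoints for the first qualifying attack with complete 2-hour data. Earlier withdrawals are absent for those reasons.
- *That someone leaving around week 6 loses the month-2 value.* With a last dose at week 4 and the end-of-study visit kept, that subject is on study for the week 8 window.
- *That the rule favours erenumab.* The direction depends on which arm loses more subjects.
- *That every missing binary outcome should simply become a failure.* This would score subjects with no qualifying attack in month 4 as triptan failures and override the MTS baseline restrictions in SAP 5.1.3.

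**Conclusion.** The conflict is real and holds on the SAP's own definitions. Followed as written, 9.5.2 removes from the MTS and MIBS-4 logistic regressions every subject whose End of Study date precedes the visit window; Table 9-3 and Protocol 9.3.4 would keep those subjects as non-responders. At week 12 this means a date before day 72, and at most about 29 subjects per arm if the planned 10% dropout is equal.

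Under assumed response rates of 50% and 35% and dropout splits of 5% and 15% either way, full NRI gives odds ratios of 1.48 to 2.14, against 1.86 under the limited rule. The sign and size of the shift rest on the unknown arm split.

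The conclusion assumes that the M-DBTP efficacy set applies to these endpoints, as SAP 6.2 says. SAP 9.5 instead assigns exploratory analyses to the E-DBTP set. If that governed, most early departures would already be gone and the phrase would matter little, so the two sections must be reconciled as well. The primary and secondary results do not depend on any of this. It should be corrected, but it does not threaten the trial's main conclusions.

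**What to change.** Before unblinding:

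1. **SAP 9.5.2:** delete the limit. State that every subject in the M-DBTP efficacy set who is eligible for the endpoint and has a missing outcome at the visit is a non-responder, as in Table 9-3. For MTS, keep the SAP 5.1.3 restrictions (non-missing baseline, and the question 3 rule for the between-attack analysis).
2. **SAP 9.5:** state that the M-DBTP efficacy set applies to the M-DBTP exploratory endpoints, in line with SAP 6.2.
3. **SAP 9.5.3:** align the wording with Table 9-3, apply NRI only to subjects with a qualifying triptan-treated attack in month 4, and exempt rescue medication use, which Table 9-3 analyses on observed data.

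If the sponsor intends the limit, the alternative is to keep it, give the denominator for each visit, amend Table 9-3 to match, and declare the change in Section 10.

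The cost is a few lines of text and no new data. Reported response rates fall slightly: in the equal-dropout illustration, from 50% and 35% to 45.0% and 31.5%.
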